Adapalene with Benzoyl Peroxide (BPO) is a unique antibiotic-free combination of Adapalene, a well-tolerated and efficacious topical retinoid, and BPO, a well-established antimicrobial agent. The complementary modes of action, efficacy and safety profiles of these two agents make Adapalene-BPO the most logical choice for once-daily treatment for all types of acne but the most severe. Adapalene possesses anti-comedogenic, comedolytic, and anti-inflammatory properties, whereas BPO, the most potent bactericidal agent, is more effective than topical antibiotics against *P. acnes*. (Brown J.M., Poston S.M. 1983) (Eady E.A., Cove J.H., Holland K.T., Cunliffe W.J. 1989) (Leyden J.J., 1983) (Lucky, A. W., 1987).

Adapalene 0.3% - BPO 2.5% gel is efficacious to treat moderate to severe acne with a trend of superiority compared to other topical preparations in subjects with severe acne (Stein Gold L., 2010). This suggests that the combination Adapalene - BPO both prevents the formation of new acne by reducing the number of primary and secondary lesions. However, it is also important to assess the local tolerability in terms of skin irritation and other skin barrier impairments in dark skin phototypes that might be caused by the treatment or by acne it-self.

Maintaining skin hydration and avoiding sun exposure is recommended as part of the skin care regimen in acne patients. Minimizing skin irritation and photo-protection can be achieved by the use of non-comedogenic moisturizers with appropriate SPF that hydrate and protect the skin from UV irradiation (Schorr E.S., 2012) (Whitney P., Bowe M.Da. 2014) (Del Rosso, J. Q., 2013) (Zeichner, J., 2011). Using an appropriate cleanser will reduce oil on the face and will not affect skin hydration or the skin barrier function.

Acne can persist for years and may affect seriously the psychosocial development, resulting in emotional problems, withdrawal from society, and depression (Koo, J Y et Smith, L L. 1991). If not treated, acne may cause serious physical and emotional scarring and can significantly impact the quality of life of those affected by the disease (Brown J.M., Poston S.M. 1983) (Usatine, R.P., 1998) Therefore this trial aims to evaluate acne medication for assessment of subject satisfaction and quality of life in the dark skin subjects known to be sensitive with topical retinoids. The local tolerance of the treatment regimen in terms of erythema, scaling, dryness, stinging/burning will also be evaluated.

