5.5. CLINICAL TRIAL VISIT DESCRIPTION AND PROCEDURES

5.5.1. Visit 1 – Baseline visit

1. Explain the nature and the constraints of the clinical trial to the subject and to his/her parent(s) or guardian if the subject is under the age of 18,
2. If a female subject of childbearing potential agrees to participate to the clinical trial, make sure she is using the required method(s) of contraception,
3. Ensure the subject (and parent/guardian for subjects under the age of 18) has read, understood, dated and signed the approved Informed Consent Form (ICF),
4. Give a dated and signed copy of the ICF to each subject and parent/guardian if applicable,
5. Question the subject about demography (birthdate, race, skin phototype, gender), relevant medical history, prior therapies (stopped within 6 months of the baseline visit and that may have an impact on the inclusion/exclusion criteria) and concomitant therapies,
6. Inform subject about authorized and prohibited concomitant therapies,
7. Check inclusion/exclusion criteria (see sections 4.3 and 4.4),
8. Log into the IVR/IWR System to check the inclusion rate in terms of balance in ethnic/race background and acne severity,
9. Conduct a urine pregnancy test (UPT) for female subjects of childbearing potential,
10. Log into the eCRF to get a Subject Identification Number (SIN),
11. Perform an Investigator's Global Assessment (IGA) of the whole face (see section 7.2.1),
12. Assess the Post-Inflammatory Hyperpigmentation (PIH) severity if any (see section 7.3.1),
13. Perform the baseline Local Tolerability Assessment (erythema, scaling dryness and stinging/burning; see section),
Note: *Stinging/burning at the baseline visit should **NOT** be assessed at baseline,*
14. Take photographs of the face according to the provided procedure (subject and parent/guardian should accept through the approved ICF),
15. Question the subject about the occurrence of any adverse events (AEs) by asking an open ended question taking care not to influence the subject's answer, such as: "have you had any new symptoms, injuries, illness or side-effects or worsening of pre-existing conditions?" Record all events as appropriate on the corresponding AE eCRF pages,
16. If the subject is eligible, assign a kit number (see specific section 0) (to be reported on the prescription form),
17. Fill in a prescription form with the Subject's Identification Number,
18. The Product Dispenser (person in charge of products dispensation) will:

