7.3. SAFETY ASSESSMENTS

Safety assessments will be conducted for all subjects at the baseline visit (after the ICF has been signed) and every subsequent visit. The safety parameters include adverse events (AEs) and increase in Post inflammatory hyperpigmentation (PIH) and local tolerance severity.

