7.3.2. Local tolerance assessment

Local cutaneous signs and symptoms (erythema, scaling, dryness and/or stinging/ burning) are possible during treatment with Adapalene 0.3% - BPO 2.5%.

The investigator will evaluate erythema, scaling, dryness and/or stinging/burning at each visit. The investigator will record stinging/burning after discussion with the subject regarding the previous application days. The investigator will ask an open-ended question, taking care not to influence the subject's answer, such as: "Have you experienced any sensations immediately following product application (within 5 minutes)?"

Erythema, scaling, dryness will be evaluated by the investigator, and stinging/burning will be recorded by the investigator after discussion with the subject. The four signs and symptoms will be graded at each follow up visit as follows:

Erythema – abnormal redness of the skin		
None	0	No erythema
Mild	1	Slight pinkness present
Moderate	2	Definite redness, easily recognized
Severe	3	Intense redness
Scaling – abnormal shedding of the stratum corneum		
None	0	No scaling
Mild	1	Barely perceptible shedding, noticeable only on light scratching or rubbing
Moderate	2	Obvious but not profuse shedding
Severe	3	Heavy scale production
Dryness – brittle and/or tight sensation		
None	0	No dryness
Mild	1	Slight but definite roughness
Moderate	2	Moderate roughness
Severe	3	Marked roughness
Stinging/Burning – pricking pain sensation immediately after dosing (within 5 minutes)		
None	0	No stinging/burning
Mild	1	Slight warm, tingling/stinging sensation; not really bothersome
Moderate	2	Definite warm, tingling/stinging sensation that is somewhat bothersome
Severe	3	Hot, tingling/stinging sensation that has caused definite discomfort

Note: *Stinging/Burning should NOT be assessed at the baseline visit*

An Adverse Event will be recorded if the severity of the signs and symptoms is such that:

- The subject's participation in the trial is interrupted at his/her request or at the investigator's request **after the first four weeks** of treatment.
- The subject permanently discontinues the treatment at his/her request or at the investigator's request.
- The subject requires concomitant prescription or OTC therapy (other than moisturizers).

Note: *Need for increased moisturizer use does NOT constitute an AE.*

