9.1.1. Variables to be statistically analyzed

The following variables will be analyzed:

Subject reported outcome variable

- *DLQI/cDLQI at Baseline, Week 12 and last visit*
- *Subject satisfaction questionnaire at Week 12 and last visit*

Efficacy variables

- *IGA score: % of subjects across scores at each visit*
- *GAI score: % of subjects across scores at Week 12 and last visit*

Safety variables on safety population

- *PIH: Raw value at each visit and % change from baseline at each post-baseline visit*
- *Local tolerance: Raw value at each visit and worst-score across visit, % of Subjects across scores at each post-baseline visit*
- *Incidence of adverse events*
- *Incidence of serious adverse events*

Other variables

- *Cosmetic acceptability questionnaire at last visit*

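### No within-subject comparison with baseline is planned for erythema, scaling and dryness, although section 7.3 defines the safety parameter as an increase, and the worst score does not say whether baseline counts

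*Combined protocol and SAP*

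**What the plan says.** Section 9.1.1 lists three summaries for local tolerance: "Local tolerance: Raw value at each visit and worst-score across visit, % of Subjects across scores at each post-baseline visit". The synopsis repeats them. The PIH entry just before it reads "PIH: Raw value at each visit and % change from baseline at each post-baseline visit".

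The assessment sections set up a comparison that these summaries do not make. Section 7.3 states: "The safety parameters include adverse events (AEs) and increase in Post inflammatory hyperpigmentation (PIH) and local tolerance severity". Visit 1 (section 5.5.1) includes the step "Perform the baseline Local Tolerability Assessment", and the flow chart in 5.4 schedules local tolerance at baseline and at all four later visits. The exception is the fourth item: "Stinging/Burning should NOT be assessed at the baseline visit" (section 7.3.2), because that symptom is defined by what is felt within minutes of applying the product.

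Section 9.1.3 adds that ordinal data get both frequencies and the usual statistics, by visit where applicable. Section 9.1.2.3 limits LOCF to GAI and IGA; other missing values stay missing. Section 9.1.4 rules out inference. Section 9.1 leaves data conventions and calculations to a separate SAP, which is not part of the text reviewed here.

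**The concern.** The protocol itself recognises that skin signs in this population have two sources. Section 2.1 speaks of irritation and "skin barrier impairments in dark skin phototypes that might be caused by the treatment or by acne it-self". Entry requires IGA 3 or 4 and at least 25 inflammatory lesions (section 4.3), and the erythema scale in 7.3.2 grades redness whatever its origin. Some subjects may therefore start with a score above zero, and redness may fall in some as acne clears while irritation appears in others.

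An increase is a statement about one subject at two times. Raw values, a worst score and score distributions each describe scores at one time or over a span. Good tolerability is one of the two parts of the hypothesis in section 3.2, so the report should be able to say how many subjects became worse than they started. As planned, it need not contain that number. If the worst score includes baseline, a subject with moderate erythema at entry and none afterwards would be reported as having moderate erythema as worst tolerance.

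**Working it through.** The plan gives no figure to reproduce: no baseline prevalence, no expected worsening, no inference. The rates below are assumptions, applied to the planned 60 subjects.

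**1. What the by-visit distributions can identify.** Let b be the share at grade 1 or more at baseline and p the share at a later visit. The share moving from 0 to 1 or more is bounded by max(0, p − b) and min(p, 1 − b).

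| b | p | Lower bound | Upper bound | Subjects of 60 |
|---|---|---|---|---|
| 0.10 | 0.50 | 0.40 | 0.50 | 24 to 30 |
| 0.30 | 0.50 | 0.20 | 0.50 | 12 to 30 |
| 0.50 | 0.50 | 0.00 | 0.50 | 0 to 30 |

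The distributions are informative when few subjects have signs at baseline and much less so when many do. In the extreme case, if 18 of 60 go from 0 to 1 while another 18 go from 1 to 0, the distribution and mean do not move, although 18/60 = 30% worsened.

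**2. The worst score if baseline counts.** With no worsening at all, the number with a worst score of 1 or more is at least 60b: 6, 18 or 30 subjects for b = 0.10, 0.30 or 0.50. If 30% worsen, independently of baseline status, the share is 1 − (1 − 0.30)(1 − b): 0.44 for b = 0.20 and 0.65 for b = 0.50. Not all of the gap to 0.30 comes from counting baseline. A sign that persists to any later visit also enters a worst post-baseline score; only signs gone by every later visit are added by the inclusive definition.

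**3. What baseline and worst score yield together.** On the inclusive reading, worst minus baseline is each subject's largest rise, or zero. Mean worst minus mean baseline is then the mean largest rise. In the 18-up, 18-down case this is 36/60 − 18/60 = 0.30. The number moving from 0 to 1 or more is also recoverable: at b = 0.20, 0.44 − 0.20 = 24% of all subjects. The total number who worsened is not. Suppose 18 subjects start with 6 each at grades 0, 1 and 2, their worst scores are 6 each at 1, 2 and 3, and the other 42 stay at 0. Either all 18 rose one grade, or 6 rose from 0 to 3 and 12 did not change. Both give a mean rise of 18/60 = 0.30 and identical tables.

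On the post-baseline reading this route closes. If the 18 improvers stay clear at every later visit and the 18 who worsened stay at grade 1, mean worst is 18/60 = 0.30, mean baseline is 18/60 = 0.30, and the difference is zero.

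**4. Whether other outputs fill the gap.** Under 7.3.2 and 8.1.1, the expected local signs become adverse events only with interruption after the first four weeks, permanent discontinuation, or added therapy other than moisturizer. Section 6.3.6 expects these reactions mostly in the first four weeks. A rise in erythema from 0 to 2 at Week 2 that meets no trigger appears only in the local tolerance tables. Any rise in PIH, by contrast, is an adverse event (7.3.1). Because missing tolerance scores are not replaced, subjects who leave early also drop out of later columns, so baseline and later columns need not describe the same people.

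**The case against.** The strongest reply is that baseline is already in the tables. Raw values at each visit include Visit 1, section 9.1.3 adds means and frequencies, and section 10.3 provides for subject listings. Group-level change can be read off, and on the inclusive reading of the worst score the mean largest rise and the number of new onsets can be derived. This stands. A reader might infer that baseline is never used, or that irritation from the gel cannot be separated at all from signs present at entry; the documents support neither. What is not reported is the number of subjects who worsened, and the derivation depends on a definition that the plan leaves open.

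Further replies also have weight:

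- Inclusion of baseline in the worst score is not stated. Section 7.3.2 speaks of grading at follow-up visits, and stinging/burning has no baseline score, so a post-baseline reading is plausible.
- Washouts (2 weeks for most topical treatments, 4 weeks for retinoids) and the exclusion of damaged facial skin, rosacea and atopic dermatitis (section 4.4) limit signs at entry, though they do not remove redness from acne.
- The separate SAP may add the comparison. But section 9.1 describes it as detailing analyses that the protocol specifies, and this one is not specified there.
- The stated purpose is subject-reported outcomes. It would be tempting to call local tolerance the main safety measure; section 7.3 names it alongside adverse events and PIH and does not rank it.

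**Conclusion.** The point holds for three of the four signs. For erythema, scaling and dryness, the plan defines the safety parameter as an increase and collects the baseline, but specifies no within-subject comparison, and its worst score is ambiguous about the baseline visit. Group-level change will be visible; the number of subjects who worsened will not be identified, and the uncertainty grows with the share who have signs at entry. On assumed rates for 60 subjects, the range runs from narrow (24 to 30) to uninformative (0 to 30). The real size is unknown, because the documents give no rates. Nothing here affects an inferential result, since none is planned.

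A reader might also expect a baseline comparison to show what the gel did. It would not: there is one arm, and every subject also receives a cleanser and a moisturizer (section 6.1.6). The comparison takes signs present at entry out of the count of worsening but does not assign a cause to what remains.

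**What to change.** In section 9.1.1, the synopsis and the SAP:

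- Define the worst score as the worst post-baseline score.
- For erythema, scaling and dryness, add the n (%) of subjects scoring above their own baseline at each post-baseline visit and at their worst post-baseline score, with the number assessed as denominator.
- Add a shift table of baseline score by worst post-baseline score for each of the three signs.
- Keep raw scores for stinging/burning and note that it has no baseline by design.

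The changes belong together. A post-baseline worst score without the shift table would give up the mean largest rise that the inclusive reading allows. The percentage form used for PIH is not a model to copy, since a percent change is undefined when the baseline score is 0.

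The cost is a few lines of text and a small set of descriptive tables. No new data, visits or subjects are needed, and the analysis stays descriptive, as section 9.1.4 requires. It should be settled before database lock, when the SAP is due to be final.

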3.2. CLINICAL HYPOTHESIS

The trial hypothesis is that daily acne treatment with Epiduo[®] Forte / TactuPump[™] Forte is well tolerated as a treatment in moderate to severe acne in dark phototypes and improves subject's quality of life.

This trial has been designed to provide evidence in support of this hypothesis.

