6.3.3. Investigational product compliance management and record

Each subject will be instructed by the Product Dispenser about the importance of being compliant with clinical trial treatment(s) throughout the clinical trial as well as the importance of returning their investigational product (used and/or not used) at week 8 and week 16 (or at the end of the trial in case of early termination) visits.

The investigational products will be collected, counted and documented on the Product Dispensation Log or other accountability document as applicable, at post-baseline visits (week 8 and week 16), by the Product Dispenser.

In this trial product compliance will be assessed using a subject diary.

At Baseline visit, subjects will be provided with a subject diary to record on a daily basis the frequency of applications of investigational product (Epiduo[®] Forte / Tactupump[™] Forte gel) and non-investigational products on the face and to record their compliance with the instructed application procedures. Subjects should return the diary at each post-baseline visit for review by the Product Dispenser. At the end of the trial week 16/early termination subjects should return the diary.

The return of investigational products should be appropriately documented on the Product Dispensation Log by the trial Product Dispenser. All subject kits will be collected at the week 16 visit at the latest, if not done before, or at Early Termination.

Subjects will also be questioned regarding the application technique, intake, frequency and missed doses of investigational product and the use of any other additional topical, systemic product as well as OTC product.

During the data review meeting, investigational product compliance for all subjects will be determined and reviewed by the sponsor's clinical team.

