6.3.6. Dose modification

Local cutaneous reactions including erythema, scaling, dryness, and stinging/burning may be experienced with use of Adapalene 0.3% - BPO 2.5%. All these adverse reactions are easily managed depending upon the severity of these adverse reactions.

Subjects should be instructed to use a moisturizer (the provided one for this trial) and if needed, investigators may reduce temporarily the frequency of the application of Adapalene 0.3% - BPO 2.5% (eg. every other day), or temporarily discontinue use.

These are most likely to occur during the first four weeks of treatment but are mostly mild to moderate in intensity, and usually improve with continued use of the medication. All dose modifications should be documented in the subject's source data and reported in the eCRF (treatment compliance page).

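### Local tolerance is tabulated without regard to dosing status, and early irritation-driven pauses and reduced use enter no stated table, so tolerance of daily treatment can be overstated

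*Combined protocol and SAP*

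**What the plan says.** Section 3.2 begins "The trial hypothesis is that daily acne treatment with Epiduo" (the brand name continues) and goes on to say that this treatment is well tolerated and improves quality of life.

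Section 6.3.6 deals with erythema, scaling, dryness and stinging/burning. If needed, "investigators may reduce temporarily the frequency of the application of Adapalene 0.3% - BPO 2.5% (eg. every other day), or temporarily discontinue use". It says of these reactions: "These are most likely to occur during the first four weeks of treatment". All dose modifications go into the source data and onto the treatment compliance page of the eCRF.

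Section 7.3.2 has the four signs graded 0 to 3 at the follow-up visits. The investigator grades erythema, scaling and dryness, and records stinging/burning after asking the subject about earlier days of application. These signs become an adverse event in three situations only: participation is interrupted after the first four weeks, treatment is stopped for good, or concomitant therapy other than a moisturizer is needed. Section 8.1.1 gives essentially the same rule.

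Section 9.1.1 lists, for the safety population (APT), "Local tolerance: Raw value at each visit and worst-score across visit", together with the percentage of subjects at each score at every visit after baseline. Section 9.1.3 lays tables out by treatment (there is one) and by visit. Under section 6.3.3 subjects keep a diary to "record on a daily basis the frequency of applications of investigational product", and compliance is reviewed at the data review meeting. Section 9 lists neither compliance nor dose modification as an analysed variable.

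**The concern.** Irritation is the reason for changing exposure, and irritation is also the outcome. Scores taken while the gel is paused or used less often therefore come selectively from subjects who reacted, and they go into the same by-visit tables as scores from subjects applying it every evening. If cutting back eases the skin, those subjects look better at the visit than they would have on daily use.

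This would matter less if the modification itself were visible elsewhere in the report, but for the period of most interest it is not. The adverse event rule starts counting interruptions only after week 4, whereas section 6.3.6 expects the reactions mainly before then. Reduced frequency alone is never a trigger. A reader of the planned output could conclude that daily use was well tolerated without learning how many subjects stayed on daily use.

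**Working it through.** The plan states no figure to reproduce: section 9.2 gives about 60 subjects with no statistical rationale, and section 9.1.4 rules out inference. The check is a reading of the sections together, followed by an illustration on assumed rates.

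**Step 1. Where would a response to irritation show up?**

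| Event | Adverse event tables (7.3.2, 8.1.1) | Any other table in section 9 |
|---|---|---|
| Pause in weeks 1–4, no added therapy, not permanent | No | None |
| Reduced frequency at any time, no added therapy | No | None |
| Interruption of participation after week 4 | Yes | – |
| Permanent discontinuation, or added therapy other than moisturizer | Yes | – |

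The first two rows are the gap. They are recorded on the eCRF compliance page (6.3.6) but not analysed.

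**Step 2. Does the worst score rescue it?** Post-baseline visits are at weeks 2, 8, 12 and 16 (5.1, 5.4). Only week 2 lies in the first four weeks, so days 15 to 28 have no scheduled assessment. From week 2 to week 8 is (8 − 2) × 7 = 42 days. A reaction already present at a visit is kept in the worst score. One that starts and is managed between visits can be missed for erythema, scaling and dryness. Stinging/burning is better protected, because the question reaches back to earlier application days.

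**Step 3. How large could the effect be?** Let
- m = share of subjects modified for irritation at a visit,
- p_d = proportion scoring 2 or more among unmodified daily users,
- p_m = the same among modified subjects, as observed,
- p_c = the same among modified subjects had they stayed on daily use.

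Pooled table: (1 − m)·p_d + m·p_m. 
Daily-use figure: (1 − m)·p_d + m·p_c. 
Gap: m·(p_c − p_m).

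The documents give none of these rates. All are assumptions, with N = 60 and p_d = 10%:

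| m (subjects) | p_m 10%, p_c 100% | p_m 30%, p_c 100% | p_m 10%, p_c 50% | p_m = p_c = 50% |
|---|---|---|---|---|
| 5% (3) | 10.0 vs 14.5 | 11.0 vs 14.5 | 10.0 vs 12.0 | 12.0 vs 12.0 |
| 10% (6) | 10.0 vs 19.0 | 12.0 vs 19.0 | 10.0 vs 14.0 | 14.0 vs 14.0 |
| 20% (12) | 10.0 vs 28.0 | 14.0 vs 28.0 | 10.0 vs 18.0 | 18.0 vs 18.0 |
| 30% (18) | 10.0 vs 37.0 | 16.0 vs 37.0 | 10.0 vs 22.0 | 22.0 vs 22.0 |

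Entries are pooled vs daily-use percentages with a score of 2 or more. Worked cell (m = 10%, p_m = 10%, p_c = 100%): 0.9 × 10 + 0.1 × 10 = 10.0; 0.9 × 10 + 0.1 × 100 = 19.0; gap 9.0 points. The gap runs from 0 to 27 points (37.0 − 10.0). It is not negative as long as pausing or reducing does not worsen irritation. Setting p_c = 100% counts every modified subject as not tolerating daily use, so it is the upper end.

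**The case against.** The strongest reply is that temporary modification is part of the regimen under section 6.3.6, so scores on all treated subjects describe tolerance of the product as it is actually used. On this view, daily treatment in section 3.2 merely names the once-daily schedule. This stands as far as it goes: the pooled tables are a legitimate description and should stay. It does not cover the absence of any count of the modifications, without which the description is incomplete.

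Much is also captured already. Later interruptions, permanent discontinuations and added therapy become adverse events, high scores at an earlier visit stay in the worst score, and the satisfaction questionnaire asks how bothersome side effects were. That is true, and it narrows the gap to the first two rows of the Step 1 table.

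Section 9.1 defers detail to a separate SAP, to be finalised before database lock. A split or count could be added there, but nothing in section 9 calls for one.

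A reader might infer more than the text supports on two points. The first is that a paused subject must arrive with a score of 0 or 1. No section says that skin recovers by the visit or that less frequent use lowers the score. The second is that stinging/burning cannot be scored during a pause and should be left blank. Section 7.3.2 ties the question to earlier application days, so blanking it could delete the very reactions of interest.

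**Conclusion.** The point holds in a limited form. Early irritation-driven pauses, and reduced frequency at any time, are collected but reported nowhere in the stated analysis. The by-visit and worst-score summaries can therefore look better than tolerance of daily treatment. The direction favours the product, provided that cutting back does not worsen irritation.

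The size cannot be estimated from the documents. The 0 to 27 points above rest wholly on assumed rates. The gap is zero if no subject is modified or if modification leaves the score unchanged. It would be too strong to say that the pooled tables are invalid or have no bearing on the hypothesis: they answer a question about the regimen with modifications allowed. This is a reporting gap in a descriptive, single-arm trial, worth closing in the SAP before database lock.

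**What to change.** Keep the local tolerance tables as planned, on the full APT. Add to section 9.1.1 or the SAP:

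1. From the eCRF treatment compliance page, the number and percentage of subjects with a reduction or pause for local reactions, with timing and duration, and with the first four weeks shown separately.
2. A composite with the full APT as denominator: worst post-baseline tolerance score of 2 or more, or any reduction, pause or discontinuation for local reactions. Show the components separately, because the composite counts every modification as a failure of daily use and is deliberately cautious.
3. A flag on by-visit scores taken during a modification, in the listing and as a footnoted count in each table.

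Leave the stinging/burning question as written. Check that the compliance page records start date, stop date and reason. The diary is described as recording frequency and adherence to the application procedure, not the reason for a missed application, so it cannot identify irritation-driven changes alone.

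The cost is a few more tables, possibly a reason field on an existing page, and a possibly less favourable tolerance figure. Because the additions use the full APT, they avoid the sparse cells that would come from splitting about 60 subjects by dosing status. The dose-modification rule in section 6.3.6 is not touched.
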